- a. Screening can be performed within 28 days prior to the study vaccination or on the day of vaccination. If screening is performed on the day of vaccination (recommended), Visit 1 and Visit 2 will coincide on Day 1. In that case, laboratory assessments should only be done once. During the screening visit, at least, all eligibility criteria must be verified prior to randomization and vaccination.
- b. If allowed by local regulations: study visits may take place at the participant's home or other location in the event of an ongoing SARS CoV 2 infection performed; visits can be performed by a trained health care professional (HCP) via phone call or a telemedicine contact.
- c. For those participants who are unable to continue participation in the study until the end of study visit, but for whom consent is not withdrawn, an early exit visit will be conducted as soon as possible. Participants who wish to withdraw consent from participation in the study will be offered an optional visit for safety follow up. For these participants only the safety assessments of the early exit visit (no blood sampling for immunogenicity) will be performed.
- d. Postpartum (PP) 1 refers to the day of pregnancy completion/termination. Visit 9 (PP 1) should occur on the day of pregnancy completion/termination or within 3 days after pregnancy completion/termination. Assessments collected the day before birth can be used, but are preferably collected on the date of birth. If the delivery takes place in a hospital where the site staff does not have privileges, it is expected that medical records are obtained to collect the applicable protocol required safety information. Blood samples are not expected in this case.
- e. Signing of the ICF should be done before any study related procedure. The ICF can be signed remotely prior to the Screening Visit. By signing the main ICF, consent is also given to follow up the neonates/infants after birth. Note: Logistics such as downloading of an application to the participant's eDevice, or accessing study materials for enrollment, are not considered a study related procedure.
- f. Check clinical status again before study vaccination.
- g. Maternal demographic information to be collected at screening includes age, race/ethnicity, and geographical location/residence.

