7.3. Participant Discontinuation/Withdrawal From the Study

A participant will be withdrawn from the study for any of the following reasons:

- Lost to follow-up
- Withdrawal of consent
- Death
- Repeated failure to comply with protocol requirements

When a participant withdraws before study completion, the reason for withdrawal is to be documented in the eCRF and in the source document. If the reason for withdrawal from the study is withdrawal of consent, then no additional assessments are allowed.

For those participants who are unable to continue participation in the study up to the last planned study visit, but for whom consent is not withdrawn, an early exit visit will be conducted as soon as possible. Participants who wish to withdraw consent from participation in the study will be offered an optional visit for safety follow-up. This includes the safety assessments of the early exit visit (no blood sampling for immunogenicity).

Withdrawal of Consent

A participant declining to return for scheduled visits does not necessarily constitute withdrawal of consent. Alternate follow-up mechanisms that the participant agreed to when signing the consent form apply as local regulations permit.

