8.2.1. Physical Examinations

A full physical examination, including height and body weight, will be carried out at screening.

At all other visits, an abbreviated, symptom-directed examination might be performed by the investigator based on any clinically relevant issues or symptoms, and medical history. Symptom-directed physical examination may be repeated if deemed necessary by the investigator.

Physical examinations will be performed by the investigator or designated medically qualified healthcare professional. Any clinically relevant abnormalities or changes in severity observed during the review of body systems should be documented in the eCRF, in accordance with Section 8.3.1.

The following physical examinations will be performed:

Full physical examination includes height, body weight^a, examination of skin, respiratory, cardiovascular, abdominal, limited neurological, musculoskeletal, external ano-genital systems (if clinically necessary), general appearance, head/ear/nose/throat, neck and extremities. This will be carried out at screening, on the day of vaccination (Study Day 1 and the Booster Visit, if applicable). A full physical examination will be performed at the Early Exit visit, if applicable.

Obstetric examination will include measurement of fundal height, fetal heart tones, determination of position of the fetus, and internal manual pelvic examination (if clinically necessary). This will be carried out at screening, on the day of vaccination (Study Day 1 [-14 days and +14 days]). If pregnant at the time of the Early Exit visit, an obstetric examination will be performed.

Obstetric ultrasound is performed by a qualified provider to confirm normal intrauterine pregnancy, estimate gestational age, and identify any fetal abnormalities as appropriate to stage of pregnancy (intrauterine growth retardation, congenital malformations).

Targeted physical examination includes an assessment of any systems that are indicated by history or observation. This will be carried out on Study Day 8 (7 days after vaccine) \pm 3 days, Study Day 29 (28 days after the vaccine) \pm 7 days, PP1, 6 months, and 12 months postpartum. If applicable, participants who receive the booster vaccination will have a targeted examination at the Day 29 PB visit.

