8.3.5. Pregnancy

All initial reports of pregnancy in participants, with onset after the PP1 visit, must be reported to the sponsor by the study site personnel within 24 hours of their knowledge of the event using the appropriate pregnancy notification form. Abnormal pregnancy outcomes (eg, spontaneous abortion, fetal death, stillbirth, congenital anomalies, ectopic pregnancy) are considered SAEs and must be reported using an SAE reporting form. Any participant who becomes pregnant after the PP1 visit will not be eligible to receive the booster vaccination. These participants will remain in the study and will continue to undergo all procedures for surveillance and follow-up of COVID-19, immunogenicity and safety as outlined in the protocol for all participants.

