Solicited local (at injection site) and systemic AEs will be summarized descriptively by group and overall. The number and percentages of participants with at least one solicited local (at injection site) or systemic AE will be presented by group and overall. The frequencies by group and overall as well as frequencies according to severity and duration will be described for solicited AEs. Frequencies of unsolicited AEs, separately for all and vaccination-related only, will be presented by System Organ Class and preferred term, while those of solicited AEs will be presented only by preferred term.

Outcomes

Adverse maternal/fetal outcomes and adverse neonatal/infant outcomes will be defined using the Case Definitions for Pregnancy Outcomes for each endpoint.

The frequency and percentage of participants for whom at least one of the indicated adverse outcomes was reported will be summarized by group and overall. For each separate adverse maternal/fetal and adverse neonatal/infant outcome, the number and percentage of participants who experience at least 1 occurrence of the given event will also be tabulated by group and overall.

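### No step requires the site to collect the pregnancy or infant outcome of a woman who leaves the study while still pregnant without withdrawing consent

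*Protocol*

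**What the plan says.** Section 7.3 deals with a participant who cannot stay to the last planned visit "but for whom consent is not withdrawn, an early exit visit will be conducted as soon as possible". Footnote c of the schedules in 1.3.1 and 1.3.2 repeats this. Section 8.2.1 anticipates an ongoing pregnancy: "If pregnant at the time of the Early Exit visit, an obstetric examination will be performed". The schedules also mark an ultrasound, adverse maternal and fetal outcomes, and adverse event recording at early exit. They list nothing after that visit.

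Other provisions bear on the point:

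- Section 7.3, on women who decline visits without withdrawing consent: "Alternate follow-up mechanisms that the participant agreed to when signing the consent form apply as local regulations permit".
- Footnote e of 1.3.1: "By signing the main ICF, consent is also given to follow up the neonates/infants after birth".
- Section 8.3.5: "All initial reports of pregnancy in participants, with onset after the PP1 visit, must be reported to the sponsor".
- Footnote d of 1.3.1 and 1.3.2 expects medical records to be obtained when delivery takes place in a hospital where site staff lack privileges.

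On withdrawal of consent, Section 7.3 says "If the reason for withdrawal from the study is withdrawal of consent, then no additional assessments are allowed", and in the next paragraph "Participants who wish to withdraw consent from participation in the study will be offered an optional visit for safety follow-up".

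**The concern.** Pregnancy outcomes, pregnancy-related adverse events, and neonatal and infant outcomes are secondary endpoints in Section 3. For a woman who exits at, say, 30 weeks, the early exit visit cannot record any of the birth outcomes, because the birth has not happened. If nobody is told to ask later, those data exist only if the site or the woman volunteers them.

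Three things raise the stakes. Enrolment has ceased, so a lost outcome cannot be replaced. Leaving during pregnancy may be connected with a complication, so the missing outcomes need not resemble the observed ones. And Section 9.5.1 lets the primary analysis proceed once adults have completed the visit about 42 days postpartum or have discontinued earlier, so the analysis need not wait for an exited woman's delivery.

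**Working it through.** **Does any other provision require the outcome?** Each candidate was read against a woman who exits pregnant, with consent intact.

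- Section 8.3.5 reports pregnancies with onset after PP1. The index pregnancy began before enrolment, so it is outside.
- Section 8.3.1 reports serious events up to the last study-related procedure, which may include a safety contact. It does not require one.
- Section 10.4.5 follows serious events unresolved at discontinuation. A stillbirth weeks after exit is a new event, not an unresolved one.
- Section 8.3.3 says adverse events, including pregnancy, are followed as set out in Section 10.4. Section 10.4 contains no step for obtaining a pregnancy outcome.
- Section 7.4 requires contact attempts before loss to follow-up is declared. Their purpose is to rescheduled missed visits and establish whether she wishes to continue; birth outcome is not named.
- Section 10.3.3 allows recontact to seek consent for additional safety evaluations. It permits, and does not require.
- The infant schedule in 1.3.3 starts at birth, and its early exit footnote concerns infants already in follow-up.
- Footnote d on delivery records is attached to Visit 9. It does not say that it applies after early exit.

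No provision forbids collection, and none requires it.

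**The plan's own figures.** Section 9.2 gives the upper 95% two-sided limit when no event is seen. The exact form is 1 − 0.025^(1/N): 8.81% for N = 40, 5.96% for 60, 3.03% for 120 and 1.53% for 240. These match the stated 8.8%, 6%, 3% and 1.5%. No stated number is in dispute.

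**Illustration of size.** The share d leaving while pregnant is not in the protocol; 5%, 10% and 20% are assumed. The background preterm rate of 8.9% and stillbirth rate of 0.6% are from Section 2.

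*If unknowns stayed in the denominator and loss were unrelated to outcome*, the shown rate is r × (1 − d):

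- 8.9% becomes 8.9 × 0.95 = 8.5%, 8.9 × 0.90 = 8.0%, 8.9 × 0.80 = 7.1%.
- 0.6% becomes 0.57%, 0.54%, 0.48%.

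*If only known outcomes counted*, the zero-event limit becomes 1 − 0.025^(1/n), with n the number known:

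- Of 40: n = 38, 36, 32 gives 9.25%, 9.74%, 10.89%, against 8.81%.
- Of 240: n = 228, 216, 192 gives 1.60%, 1.69%, 1.90%, against 1.53%.
- Of the 22 in the Sentinel and Safety Cohorts: n = 21, 20, 18 gives 16.11%, 16.84%, 18.53%, against 15.44%.

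*If loss were related to outcome*: assume 40 women, 4 leavers with a 25% risk, and 36 others at 8.9%. Expected events are 36 × 0.089 + 4 × 0.25 = 3.2 + 1.0 = 4.2, so the full rate is 4.2/40 = 10.5%. Observed events are 3.2, giving 3.2/40 = 8.0% on all women and 3.2/36 = 8.9% on women with a known outcome. Changing the denominator alone recovers less than half of the gap. Collecting the outcome closes it.

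**The case against.** The strongest reply is that the protocol already leaves room for later contact. Alternate follow-up agreed in the consent form applies to women who decline visits, infant follow-up consent is given at entry, and serious pregnancy complications unresolved at exit must be followed. Section 8.2 also requires clinically significant abnormalities persisting at early withdrawal to be followed. The infant is a participant with its own schedule, and nothing says that the mother's exit ends the infant's participation. The limit in 8.3.5 is deliberate, since the main schedule covers the index pregnancy at Visit 9.

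Most of this stands, and it rules out saying that there is no later contact. It does not supply a requirement: the alternate mechanisms are undefined and do not name birth outcome, and follow-up of an unresolved event does not reach a new one. Visit 9 covers the index pregnancy only for a woman still on the schedule.

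A reader might also infer that women with unknown outcomes are counted as event-free, because adult safety uses FAS-A (all vaccinated adults) and Section 9.4.2 says that "the number and percentage of participants who experience at least 1 occurrence of the given event will also be tabulated by group and overall". The protocol does not state this. Handling of unknown outcomes is commonly left to the SAP, which is not shown. Pregnancy outcome is categorical, so an unknown falls in no category. An infant never recorded would in practice be absent from FAS-NVN, not event-free within it.

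On consent withdrawal, it can be argued that the optional visit comes before withdrawal takes effect. That reading is possible, but the text does not say so.

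**Conclusion.** The gap is real but limited. For early exit during pregnancy without withdrawal of consent, the protocol requires one visit timed by departure and specifies no later collection of the pregnancy outcome or infant status. Secondary-endpoint data may therefore go uncollected, possibly selectively, and no later analysis could recover them.

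The documents do not support the stronger conclusions that later contact is excluded, that unknown outcomes are counted as event-free, or that reported rates will be biased low. The relative reduction of 5% to 20% holds only under assumed non-informative loss of the same size and only if unknowns stay in the denominator. The 10.5% example rests on an assumed number of women, number of leavers and risk among them. Neither the number finally enrolled nor any dropout rate is stated, and the 8.9% comes from a general population, whereas Section 5.2 excludes multiple and higher-risk pregnancies. The study is descriptive, so no test is affected. This is a cheap improvement worth making, not a flaw in the design as a whole.

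**What to change.** In Section 7.3 and in footnote c of 1.3.1 and 1.3.2, add: for early exit before pregnancy completion without withdrawal of consent, the site obtains the pregnancy outcome, delivery history and neonatal status by telephone or from medical records after the expected delivery date, as consent and local regulations permit; the infant may continue under 1.3.3. Apply this also to women who have already exited, where their consent allows it.

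Beside the outcome percentages in Section 9.4.2, report the number of women whose pregnancy outcome is unknown, by group and overall.

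Reconcile the two sentences in Section 7.3 on consent withdrawal, and the matching part of footnote c, so that sites have one rule on whether and when the optional safety visit can take place.

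The cost is one call or chart request per woman who exits while pregnant, plus short protocol and consent-form wording. Some women may decline, and their number would then be visible.

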7.3.1. Withdrawal From the Use of Research Samples

Withdrawal From the Use of Samples in Future Research

The participant may withdraw consent for use of samples for research (refer to long-term retention of samples for additional future research in Section 10.3). In such a case, samples will be destroyed after they are no longer needed for the clinical study. Details of the sample retention for research are presented in the main ICF.

7.4. Lost to Follow-up

To reduce the chances of a participant being deemed lost to follow-up, attempts should be made to obtain contact information from each participant, eg, home, work, and mobile telephone numbers and e-mail addresses for both the participant as well as appropriate family members. A participant (adult, neonate, and infant) will be considered lost to follow-up if they repeatedly fails

to return for scheduled visits and is unable to be contacted by the study site after multiple documented attempts.

A participant (adult, neonate, and infant) cannot be deemed lost to follow-up until all reasonable efforts made by the study site personnel to contact the participant are deemed futile. The following actions must be taken if a participant fails to return to the study site for a required study visit:

- The study site personnel must attempt to contact the participant to reschedule the missed visit as soon as possible, to counsel the participant on the importance of maintaining the assigned visit schedule, to ascertain whether the participant wishes to or should continue in the study.
- Before a participant is deemed lost to follow-up, the investigator or designee must make every reasonable effort to regain contact with the participant (where possible, 3 telephone calls, e-mails, fax, and, if necessary, a certified letter to the participant's last known mailing address, or local equivalent methods). Locator agencies may also be used as local regulations permit. These contact attempts should be documented in the participant's medical records.
- Should the participant continue to be unreachable, they will be considered to have withdrawn from the study.

Should a study site close, eg, for operational, financial, or other reasons, and the investigator cannot reach the participant to inform them, their contact information may be transferred to another study site.

8. STUDY ASSESSMENTS AND PROCEDURES

Overview

The Schedules of Activities (Section 1.3) summarize the frequency and timing of safety, reactogenicity, immunogenicity, and other measurements applicable to this study. All participants or parent(s)/caregiver(s) (in case of neonates/infants) in the study will be counselled on COVID-19 infection at any interaction with study site staff in line with local guidelines.

All adult participants will be provided access to an eCOA. The eCOA device will be used to collect (suspected) COVID-19 signs and symptoms surveillance information (Symptoms of Infection with Coronavirus-19 [SIC], including body temperature, and pulse oximetry results) at baseline and in case of COVID-19-like signs and symptoms.

All eCOA assessments should be conducted/completed before any tests, procedures, or other consultations to prevent influencing participant responses. Parents/caregivers should also perform (suspected) COVID-19 surveillance (symptom check) and record any signs or symptoms that are suggestive of possible COVID-19 for the neonate/infant and complete the ObsRO for the Pediatric Symptoms of Infection with Coronavirus-19 [PedSIC], including the highest body temperature recorded within 24 hours, blood oxygen saturation levels, and pulse rate, in the eCOA. Procedures for adult participants and neonates/infants with (suspected) COVID-19 are outlined in Section 1.3.4 and Section 1.3.5, respectively.

Adult participants will be provided with a thermometer (to measure body temperature), ruler (to measure local injection site reactions) to record body temperature and solicited local (at injection site) and systemic signs and symptoms in the eCOA device. Parent(s)/caregiver(s) will be provided with a separate thermometer for the neonate/infant to record body temperature for the neonate/infant in the eCOA, in the event of confirmed or suspected COVID-19.

The site staff will be provided with ePRO and ObsRO completion guidelines that includes instructions on capturing responses in the eCOA and grading scales to assess severity of the signs and symptoms after vaccination (reactogenicity). The study staff is responsible for providing appropriate training to the participant/parent(s)/caregiver(s) to prevent missing or incorrect data. The reactogenicity diary will be reviewed by the study personnel at the Day 8 visits indicated in the Schedule of Activities (Section 1.3.2 and Section 1.3.3, respectively). If the reactogenicity diary review is missed/unavailable at Day 8, the reactogenicity diary will be reviewed during the following visit.

Sites should reach out to a participant if the participant fails to complete any of the questions displayed in the eCOA. The questionnaire will be accessible on the eCOA platform in between scheduled reminders and participants will be encouraged to answer the surveillance question in the eCOA as soon as possible after the onset of COVID-19-like symptoms, or any other symptoms with new onset, including those listed above. Every effort will be made to document the status of all participants that are lost to follow-up due to not completing the eCOA and for whom hospitalization has not been recorded.

If multiple assessments are scheduled for the same timepoint, it is recommended that procedures be performed in the following sequence: (a) for adult participant: physical/obstetric examination and vital signs, ultrasound blood draws, and vaccination; (b) for neonate/infant: physical examination and vital signs, blood draws. If needed, assessments may be performed at another day within the applicable visit window. Actual dates and times of assessments will be recorded in the source documentation and eCRF.

Adult participants will also be provided with a kit to collect nasal swabs at Day 1 to be used in case they experience COVID-19-like symptoms during the study (see Section 8.1.2). In the event of the neonate/infants developing COVID-19 like symptoms, the parent(s)/caregiver(s) should contact the site, who will provide a trained HCP to collect nasal swabs from the neonate/infant.

If allowed by local regulations, study visits other than screening and vaccination visit may take place at other locations if there are travel restrictions in case of exceptional situations (eg, pandemic).

Blood Collection - Adult Participants

The maximum total blood volume (without blood samples for PBMCs) to be collected over the course of the study is approximately 166 mL from adult participants receiving 1 dose of Ad26.COV2.S at 5×10^{10} vp.

The maximum total blood volume collected over the course of the study including blood samples for isolation of PBMC for assessment of cellular immunity is approximately 256 mL from adult participants who were enrolled in the PBMC subset of the study.

An additional 60 mL of blood will be collected from participants who receive the booster vaccination.

Further information is provided summarized in [Table 1](#).

Table 1: Maximum Volume of Blood to be Collected from Each Participant

Type of Sample	Volume per Sample (mL)	No. of Samples per Participant 1-dose	Approximate Total Volume of Blood (mL) ^a 1-dose
Adults			
Safety laboratory assessments (hematology, chemistry)	6.5	Max 7	Max 45.5
Humoral Immunogenicity (serum), serology testing (SARS-CoV-2 Abs)	10	4	40
Serological Analysis of anti-SARS-CoV-2 antibodies	2.5	4	10
Plasma collection (safety+immunogenicity)	5	5	25
Serum collection (safety)	7.5	5	37.5
Biomarkers vaccine-related (whole peripheral blood) PAXgene [®]	2.5	3	7.5
Cellular Immunogenicity (PBMC) subset	30	3	90
Approximate total for adults excluding participants in the PBMC subset			Max 165.5
Approximate total for subset of adults with blood for PBMC collection			Max 255.5
Adults - additional blood draws in case of (suspected) COVID-19			
Humoral Immunogenicity (serum)	10	2	20
Biomarkers PAXgene [®]	2.5	2	5
Adults - additional blood draws in case of (suspected) AESI			
Clinical laboratory blood sample (whole blood)	15	2	30
Neonates and infants			
Humoral Immunogenicity (serum) ≤6 months of age	3.5	2	7
Approximate total for infants			7
Neonates and infants - additional blood draws in case of (suspected) COVID-19			
Humoral Immunogenicity (serum)	2.5	2	5
Neonates cord blood			
Humoral Immunogenicity (cord blood)	15 ^b	1	15 ^c
Biomarkers (cord blood) PAXgene [®]	2.5	1	2.5
Approximate (minimum) total			17.5
Adults - Additional blood draws in case of receiving the booster vaccination			
Clinical blood sample (safety, whole blood)	15	2	30
Humoral Immunogenicity (serum)	10	2	20
Serological Analysis of anti-SARS-CoV-2 antibodies	2.5	2	5
Biomarkers vaccine-related (whole peripheral blood) PAXgene [®]	2.5	2	5
Approximate additional total in case of receiving the booster vaccination			60

a. Calculated as number of samples multiplied by amount of blood per sample. Repeat or unscheduled samples may be taken for safety reasons or technical issues with the samples.

b. Approximately 15 mL (minimum of 10 mL).

Visit Windows

Visit windows that will be allowed are provided in Section 1.3 and summarized below. The participant should be encouraged to come on the day planned but using the visit window is allowed. The timings of the post-vaccination visits will be determined relative to the actual day of the corresponding vaccination. If a participant misses a vaccination or has a delayed vaccination, the post-vaccination visits will be calculated from the imputative vaccination date according to protocol.

If a vaccination window is missed, efforts will be made to vaccinate and collect samples from the participant, even if out of window. The timings of the post-vaccination visits will be determined relative to the actual day of the vaccination, unless they overlap with other scheduled visits. If so, it would be evaluated in a case-by-case basis in which case the sponsor should be contacted, and a case-by-case assessment agreed.

Screening

Screening will be performed within 28 days prior to study vaccination or on the day of vaccination. If screening is performed on the day of vaccination, study visits will be combined (ie, for adult participants, Visits 1 and 2 will occur on Day 1). Screening must be completed, and all eligibility criteria must be fulfilled prior to vaccination. Participants may be rescreened only once (see Section 5.4).

The nasal swab for the RT-PCR test for the presence of SARS-CoV-2 infection must be done within 4 days before vaccination and repeated pre-vaccination if necessary. The study-specific ICF date will be entered into the eCRF.

Sample Collection and Handling

The actual dates and times of sample collection must be recorded in the eCRF or laboratory requisition form. Refer to Section 1.3 for the timing and frequency of all sample collections.

Instructions for the collection, handling, storage, and shipment of samples can be found in the laboratory manual that will be provided. Collection, handling, storage, and shipment of samples must be under the specified, and where applicable, controlled temperature conditions as indicated in the laboratory manual.

Study-Specific Materials

The investigator will be provided with the following supplies:

- Latest version of the Ad26.COVS Investigator Brochure and Addenda
- Thermometer (for adults and neonates/infants)
- Ruler (to measure diameter of any erythema and swelling)
- An approved pulse oximeter (for adults and neonates/infants)
- Pharmacy manual/SIPPM

- Laboratory manual
- IWRS Manual
- eCRF completion guidelines
- Sample ICF
- Nasal swab kit, and participants instructions
- eCOA platform access and participant instructions (participants may use their own eDevice using an application if their device [smartphone or tablet] is compatible, or a web portal). Provisioned devices will be available on a limited basis. Adult participant reactogenicity diaries and the latest Independent Ethics Committee/Institutional Review Board (IEC/IRB)-approved versions of the PedSIC/SIC are part of the eCOA
- Contact information page(s)
- Tablet for eConsent, if applicable

